9.2. Setting

The study population will be extracted from MDV, a comprehensive resource based on hospital claims data and Diagnosis Procedure Combination (DPC) data. Information on demographics, mortality, laboratory tests, IP, OP, and ED claims, treatments, procedures, and costs are available for approximately 50 million patients. Patients will be identified using the inclusion and exclusion criteria listed in Sections 9.2.1 and 9.2.2. The inclusion and exclusion criteria ensure the study captures patients with MM who initiate elranatamab treatment in RW setting after its approval date in Japan. The exclusion criterion removes patients treated within clinical trials to avoid bias from controlled study conditions and ensure generalizability to routine clinical practice. These criteria may limit the number of eligible patients, especially early in the elranatamab post-approval period.

Index date: defined as the date of first hospital claim with elranatamab administration after March 26, 2024.

44mg/1.1mL vial of elranatamab: hospital claim of elranatamab with vial size of 44mg/1.1mL which corresponds to an SUD dose or a partial dose.

76mg/1.9mL vial of elranatamab: hospital claim of elranatamab with vial size of 76mg/1.9mL which corresponds to a full dose.

Study period: defined as the period between start of data availability to end of data availability in MDV.

Baseline period: defined as the variable period between MM diagnosis and first hospital claim of elranatamab administration (index date).

Medical history assessment window: defined as the 365-day window prior index date. If a patient has fewer than 365 days of data available prior to the index date, the assessment window will be equal to the maximum number of days available prior to the index date.

CCI assessment windows: defined as (1) the 180-day window prior index date and (2) the 365-day window prior to index date. If a patient has fewer than 180 days, or 365 days of data available prior to the index date, the assessment window will be equal to the maximum number of days available prior to the index date.

HCRU baseline assessment period: defined as the 180-day window prior index date. If a patient has fewer than 180 days of data available prior to the index date, the assessment window will be equal to the maximum number of days available prior to the index date.

SUD period: defined as the period between a patient's first 44mg/1.1mL vial of elranatamab and first 76mg/1.9mL vial of elranatamab, inclusive. See Section 9.3.1 and Annex 1 for more details. Within the SUD period, three sub-periods are identified:

- **Overall:** defined as the period between first 44mg/1.1mL vial and first 76mg/1.9mL vial of elranatamab.
- **First 44mg/1.1mL vial – Second 44mg/1.1mL vial:** defined as the period between the two 44mg/1.1mL vials of elranatamab, if second 44mg/1.1mL vial is administered.
- **Second 44mg/1.1mL vial – first 76mg/1.9mL vial:** defined as the period between the second 44mg/1.1mL vial and the first 76mg/1.9mL vial of elranatamab, if second 44mg/1.1mL vial is administered.

Follow-up period: defined as the period between the first hospital claim for elranatamab (index date) and the end of the hospital claim of the last elranatamab administration. Within this follow-up period, five sub-periods are identified (when sufficient follow-up time is available at the patient level). These sub-periods allow for reporting study endpoints across different phases of the follow-up period, and are based on expected dosing administrations and schedule of patients with switch to bi-weekly administrations from label guidance (see [Table 10. Dosing Schedule of Elranatamab during Follow-up Period for Patients Switching to](#)

[Q2W](#) and [Table 11. Dosing Schedule of Elranatamab during Follow-up Period for Patients staying on QW](#)):

- **Index date to day 8:** defined as the first 8 days post-index date, inclusive. Also defined as day 1 to day 8.
- **Day 9 to day 168:** defined as the period from day 9 to day 168 post-index date.
- **Day 169+:** defined as the period from day 169 post-index date to end of follow-up period.

- **Overall follow-up:** defined as the period from index date to end of follow-up period.

IVIG follow-up assessment period: defined as the 30-day window post index date. If a patient has fewer than 30 days of data available post to the index date, the assessment window will be equal to the maximum number of days available post to the index date.

CRS/ICANS follow-up assessment period: defined as the 14-day window post index date. If a patient has fewer than 14 days of data available post to the index date, the assessment window will be equal to the maximum number of days available post to the index date.

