- **Study design:** This is a retrospective observational study utilizing de-identified data from Japan Hospital administrative claims data (Medical Data Vision [MDV]).
- **Population:** The study population will include all adults aged 18 years or older with an MM diagnosis who initiate elranatamab on or after March 26, 2024 (PMDA Elrexfio approval date). Patients with evidence of clinical trial participation will be excluded.
- **Variables:** The following variables will be summarized and reported:

Exposure of interest:

Exposure is defined as at least one record of a hospital claim for elranatamab on or after March 26, 2024. All patients included in the study will be considered exposed. Analyses of outcomes during the SUD period will also be stratified based on types of elranatamab exposure during that time (i.e., complete and timely SUD, complete but not timely SUD, alternative SUD). Clinical data will be collected from MDV hospital data.

Study outcomes:

Study endpoints include: elranatamab timing and dosing (i.e., types of doses, time between doses, relative administration intensity), HCRU and costs (i.e., IP/OP/ED claims and associated costs, degree of nursing), other MM treatment post elranatamab administration (i.e., PIs, SCT, supportive therapy), known adverse events (i.e., CRS events occurrence, frequency and associated length of stay, time from index to CRS event), infection (i.e., infection occurrence, time from index to infection, antibiotics), and supportive medication (i.e., IVIG, acetaminophen, dexamethasone).

Covariates:

Covariates will include baseline demographics (i.e., age, sex, weight etc.), and baseline clinical characteristics (i.e., comorbidities and treatment history).

- **Data sources:** The MDV database is a comprehensive resource containing administrative data from over 540 hospitals in Japan. This dataset includes information on demographics, mortality, labs, IP, OP, ED claims, treatments, procedures and costs of approximately 50 million patients. MDV is an aggregated, de-identified dataset where no patient can be individually identified and therefore no patient consent is required.
- **Study size:** This is a retrospective descriptive study with no a priori hypotheses; therefore, sample size calculations are not applicable. As of February 2025, MDV included 128 patients that had at least one hospital claim for an elranatamab administration.

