8. RESEARCH QUESTIONS AND OBJECTIVES

Research Question: What are the characteristics of adult patients with MM who initiate elranatamab in Japan, and the SUD process, treatment patterns, HCRU, and safety associated with elranatamab administration?

The following objectives will be assessed among patients with MM receiving elranatamab:

Primary objectives:

- Objective 1: To describe patients with MM initiating elranatamab, including demographics, treatment and medical history.
- Objective 2: To describe and characterize elranatamab utilization, including timing, administration and dosing, during the follow-up period, including the step-up dosing (SUD) period.

Secondary objectives:

- Objective 3: To describe HCRU and costs associated with elranatamab usage during the follow-up period, including the SUD period.
- Objective 4: To describe the use of other treatments for MM including supportive therapy during the follow-up period.
- Objective 5: To describe incidence and prevalence of cytokine release syndrome (CRS), immune effector cell associated neurotoxicity syndrome (ICANS), and cytopenias during the SUD period.
- Objective 6: To describe infection incidence and prevalence during the follow-up period.

Exploratory objectives:

- Exploratory Objective 1: To describe the use of supportive medications during the SUD period and administration of IVIG within the 30-day post-index period.

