			Number of top 5 department visits claims PPPM Note that the top 5 will not be established a priori, but rather will be determined based on the data and sample	HCRU baseline period Follow-up period (overall only)
			Number of top 5 department visits claims PPPD Note that the top 5 will not be established a priori, but rather will be determined based on the data and sample	SUD period

090177e1a4a71ff1\Approved\Approved On: 05-Nov-2025 14:15 (GMT)

Variable	Role	Data Source	Operational Definition	
			Definition	Assessment Period(s)
Degree of nursing	Outcome	MDV	Highest degree of nursing recorded (categorical), N (%) For the following categories: No support, Support level 1, Support level 2, Care level 1, Care level 2, Care level 3, Care level 4, Care level 5, Is applying, Unknown	HCRU baseline period SUD period Follow-up period (overall only)

Abbreviations: ED: emergency department; HCRU: healthcare resource utilization; IP: inpatient; OP: outpatient; PPPD: per patient per day; PPPM: per patient per month; SUD: step-up dosing.

Table 6. Variables for Outcomes (Objective 4 - Other MM treatments including supportive therapy)

Variable	Role	Data Source	Operational Definition	
			Definition	Assessment Period(s)
PIs	Outcome	MDV	Health claim code for bortezomib, carfilzomib, or ixazomib (Yes/No) Health claim code for each PI will also be reported.	Follow-up period
IMiDs	Outcome	MDV	Health claim code for lenalidomide, thalidomide, or pomalidomide (Yes/No) Health claim code for each IMiD will also be reported.	Follow-up period
anti-CD38s	Outcome	MDV	Health claim code for daratumumab, or isatuximab (Yes/No)	Follow-up period

Variable	Role	Data Source	Operational Definition	
			Definition	Assessment Period(s)
			Health claim code for each anti-CD38 will also be reported.	
SCT	Outcome	MDV	Health claim code for SCT (Yes/No) Health claim code for each SCT (allogeneic and autologous) will be reported.	Follow-up period
CAR-T	Outcome	MDV	Health claim code for idecabtagene vicleucel or ciltacabtagene autoleucel (Yes/No) Health claim code for each CAR-T will be reported.	Follow-up period
Chemotherapies	Outcome	MDV	Health claim code for chemotherapies (doxorubicin hydrochloride, melphalan, bendamustine, cyclophosphamide, etoposide, or cisplatin) (Yes/No) Health claim code for each chemotherapy will also be reported.	Follow-up period
IVIG	Outcome	MDV	Health claim code for IVIG (Yes/No)	Follow-up period

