Days from index to first ICANS event	Outcome	MDV	Time in days from index date to first ICANS event (continuous)	CRS/ICANS follow-up assessment period
Cytopenia occurrence ¹	Outcome	MDV	Disease code or labs value for cytopenias occurrences (Yes/No): 
 Anemia Leukopenia Lymphopenia Neutropenia Thrombocytopenia Number and proportion of patients with a health claim code for each cytopenia will also be reported. Incidence and prevalence will be reported, see Section 9.7.2 for additional details.	SUD period
Days from index to first cytopenia	Outcome	MDV	Time in days from index date to first cytopenia (continuous)	SUD period

090177e1a4a71ff1\Approved\Approved On: 05-Nov-2025 14:15 (GMT)

Abbreviations: CRS: cytokine release syndrome; ICANS: Immune effector Cell Associated Neurotoxicity Syndrome; SUD: step-up dosing.

Notes:

1. Variable will be measured as incident and prevalent. Incident cases have a 30-day washout period applied.

Table 8. Variables for Outcomes (Objective 6 - Infections)

Variable	Role	Data Source	Operational Definition	
			Definition	Assessment Period(s)
Infection occurrences ¹	Outcome	MDV	Disease code for infections; the list of infections of interest will be outlined in the SAP (Yes/No) Incidence and prevalence will be reported, see Section 9.7.2 for additional details.	Follow-up period
Days from index to infection	Outcome	MDV	Time in days from index date to first infection (continuous)	Follow-up period
Days between infections	Outcome	MDV	Days between infection claims (continuous) For patients with ≥ 2 disease code for infections listed in the SAP during the time period	Follow-up period

Variable	Role	Data Source	Operational Definition	
			Definition	Assessment Period(s)
Antibiotics	Outcome	MDV	Health claim code for antibiotic treatment (Yes/No)	Follow-up period
Antivirals	Outcome	MDV	Health claim code for antiviral treatment (Yes/No)	Follow-up period
Antifungals	Outcome	MDV	Health claim code for antifungal treatment (Yes/No)	Follow-up period

Notes:

1. Variable will be measured as incident and prevalent. Incident cases have a 60-day washout period applied.

Table 9. Variables for Outcomes (Exploratory Objective 1 – Supportive Medications)

Variable	Role	Data Source	Operational Definition	
			Definition	Assessment Period(s)
Dexamethasone	Outcome	MDV	Health claim code for dexamethasone (Yes/No)	SUD period
Diphenhydramine	Outcome	MDV	Health claim code for diphenhydramine (Yes/No)	SUD period

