9.7.3. Relative Administration Intensity

RAI will be calculated as the cumulative frequency of administration received over the expected number of administrations. Since response is needed to determine if switching to bi-weekly doses is appropriate and is not available in MDV, two schedule definitions will be used to estimate the expected number of administration to calculate RAI (Table 10. Dosing Schedule of Elranatamab during Follow-up Period for Patients Switching to

Q2W and Table 11. Dosing Schedule of Elranatamab during Follow-up Period for Patients staying on

QW Table 10. Dosing Schedule of Elranatamab during Follow-up Period for Patients Switching to

Q2W).

$$\text{RAI} = \frac{\text{Number of administrations received}}{\text{Number of expected administrations during the time period}}$$

a) Schedule 1¹

Assumption that all patients switch to bi-weekly doses (Q2W) after day 169 post-index.

Table 10. Dosing Schedule of Elranatamab during Follow-up Period for Patients Switching to Q2W

Follow-up Sub-Periods	Expected Administrations	Vial Size
Index date - Day 8	3 administrations	2 x 44mg/1.1mL 1 x 76mg/1.9mL
Day 9 - Day 168	1 administration per week	76mg/1.9mL
Day 169 – End of follow-up	1 administration every two weeks	76mg/1.9mL

Notes:

090177e1a4a71ff1\Approved\Approved On: 05-Nov-2025 14:15 (GMT)

¹ Adapted from dosing and administration guidance of the Japanese elranatamab label available at <https://labeling.pfizer.com/ShowLabeling.aspx?id=20462>

b) Schedule 2¹

Assumption that all patients continue with weekly doses (QW) after day 169 post-index.

Table 11. Dosing Schedule of Elranatamab during Follow-up Period for Patients staying on QW

Follow-up Sub-Periods	Expected Administrations	Vial Size
Index date - Day 8	3 administrations	2 x 44mg/1.1mL 1 x 76mg/1.9mL
Day 9 – End of follow-up	1 administration per week	76mg/1.9mL

Notes:

¹ Adapted from dosing and administration guidance of the Japanese elranatamab label available at <https://labeling.pfizer.com/ShowLabeling.aspx?id=20462>

Treatment exposure will be assessed across the different follow-up periods. End of follow-up is defined as the end of the hospital claim of the last elranatamab administration inclusive.

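### Follow-up closes with the claim carrying the last elranatamab dose, so myeloma therapy begun afterwards (Objective 4) is excluded by definition, and infections and resource use after that claim (Objectives 6 and 3) go uncounted

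*Protocol*

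**What the plan says.** Section 9.2 defines follow-up as running between the first elranatamab claim "and the end of the hospital claim of the last elranatamab administration". Section 9.1 gives the same rule, and Section 9.7.3 restates it: "End of follow-up is defined as the end of the hospital claim of the last elranatamab administration inclusive".

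Three secondary objectives in Section 8 use this window:

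- The fourth, on other treatment, reads "To describe the use of other treatments for MM including supportive therapy during the follow-up period".
- The sixth, on infections, reads "To describe infection incidence and prevalence during the follow-up period".
- The third, on resource use, reads "To describe HCRU and costs associated with elranatamab usage during the follow-up period, including the SUD period".

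Table 2 and Tables 5, 6 and 8 apply it. The abstract, under study outcomes, describes the Objective 4 endpoint as "other MM treatment post elranatamab administration (i.e., PIs, SCT, supportive therapy". Table 6 lists PIs, IMiDs, anti-CD38s, SCT, CAR-T, chemotherapies and IVIG. The CAR-T row, for example, reads "Health claim code for idecabtagene vicleucel or ciltacabtagene autoleucel (Yes/No", assessed over follow-up. The infection row of Table 8 reads "Disease code for infections; the list of infections of interest will be outlined in the SAP (Yes/No", assessed over the same period.

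**The concern.** A single definition suited to dosing variables also decides what can be seen of later treatment, infections and cost.

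- **Objective 4.** A next line normally starts after the previous drug stops. Under this rule it falls outside the window. A Yes/No table would then read as No for patients who did receive further therapy, and a reader of the abstract could take that as evidence that little was given.
- **Objectives 6 and 3.** An infection that stops treatment, and the care it requires, lies outside unless it falls in the same claim as the last dose. The end of follow-up can then depend on the very event being counted, in a study that the sponsor has designated a post-authorization safety study.

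**Working it through.** The protocol gives no figure that depends on this definition, so there is none to reproduce. The check compares the definition with each window that uses it, followed by an illustration under stated assumptions.

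**1. Windows after index, from Section 9.2 and Tables 2 and 5 to 9**

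| Endpoint | Window after index | Tied to the last dose? |
|---|---|---|
| Objective 3, resource use and cost | SUD period; follow-up | Follow-up: yes |
| Objective 4, other MM treatment | Follow-up only | Yes |
| Objective 6, infections | Follow-up only | Yes |
| Objective 5, CRS and ICANS | 14 days from index | No |
| Exploratory objective, IVIG | 30 days from index | No |

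The last two windows are shortened only where fewer days of data are available. The study period itself runs to the end of MDV data (Section 9.2), so the truncation comes from the definition and not from the data source. Section 9.9 does not list it as a limitation, and Section 9.7.6 plans no sensitivity analysis.

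**2. What is inside and outside**

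- Inside: therapy given together with elranatamab, therapy during interruptions, and anything up to the end of the last-dose claim.
- Outside: everything after that claim. Capture of therapy begun there is 0% by definition.
- An infection that only delays the next dose is inside. The same infection, if no further dose follows, is outside unless coded in the last-dose claim. This is why the end of follow-up can be informative.
- If the last dose is given in hospital, the claim may include the rest of the stay. The protocol does not say when an outpatient claim ends. If it closes on the day, nothing follows the dose, and the tail depends on care setting.

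**3. One hypothetical patient.** Suppose the last dose is on day 8, given as an outpatient, with the claim closing that day (an assumption). CRS on day 12 counts and an infection on day 12 does not. IVIG on day 20 counts under the exploratory objective and does not count under Objective 4.

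**4. Illustration of unobserved time.** Let L be the day of the last dose and g an assumed post-treatment window. Neither g nor same-day closure of the claim is in the protocol. Unobserved share = g / (L + g).

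| L (day) | g = 30 | g = 60 | g = 90 |
|---|---|---|---|
| 1 | 30/31 = 96.8% | 60/61 = 98.4% | 90/91 = 98.9% |
| 8 | 30/38 = 78.9% | 60/68 = 88.2% | 90/98 = 91.8% |
| 84 | 30/114 = 26.3% | 60/144 = 41.7% | 90/174 = 51.7% |
| 168 | 30/198 = 15.2% | 60/228 = 26.3% | 90/258 = 34.9% |

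The share is largest in patients who stop early. These are shares of time, not of events, and they apply only to patients who stopped at least g days before their data end.

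**The case against.** The strongest reply is that the window is an on-treatment window and the numbered objectives agree with it. Objectives 4 and 6 are expressly limited to follow-up, and Objective 3 concerns costs associated with elranatamab use. The sub-periods follow the dosing schedule, and Tables 2, 5, 6 and 8 are consistent. No numbered objective promises next-line therapy or safety after discontinuation. The abstract's phrase might also mean after an administration, that is after index, since supportive therapy appears in the same bracket.

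Much of this stands. For Objectives 3 and 6 an on-treatment description is defensible if it is labelled as such, and the protocol does not label it. For Objective 4 the reply is weaker. The abstract's wording most naturally points to later treatment, and SCT and CAR-T would seldom fall between two elranatamab doses.

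Three stronger readings are tempting and are not supported:

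- **That Objective 4 will be empty.** It will not: concomitant use, use during interruptions and use later in the last-dose claim are all recorded. Patients still on treatment at the data cut have a last dose near the end of data and lose little. Their share is not given.
- **That the infection loss can be sized.** If 5% to 15% of the 128 patients in Section 9.5 stopped for an infection coded after the last claim, that would be 0.05 × 128 = 6.4 to 0.15 × 128 = 19.2 patients. The protocol gives no basis for that range. Because the Table 8 variable is Yes/No, a patient with an earlier infection inside the window already counts, so even under the assumption the figure is an upper bound.
- **That one outpatient dose gives exactly one day of follow-up.** This needs the claim to close the same day, which the protocol does not state.

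**Conclusion.** The point holds as a should-fix, centred on Objective 4. As written, therapy begun after the last-dose claim is excluded by definition. That conflicts with the abstract's description of the endpoint and leaves the SCT and CAR-T rows largely uninformative. Infections and resource use after that claim are also missed, including infections that lead to stopping, so the end of follow-up can be informative and may differ by care setting. The size of the effect on infection and cost results cannot be derived from the protocol.

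The affected objectives are all secondary and the study is descriptive. Objective 1 is unaffected, and the present definition suits the dosing variables of Objective 2. The conclusion rests on the text of Sections 9.1, 9.2 and 9.7.3 and the tables; Figure 1 is not reproduced in the text at hand and could not be checked.

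**What to change.** - Keep the present definition as the on-treatment period for dosing variables and relative administration intensity.
- For Objective 4, add an observation window from index to the earliest of death, last record at the hospital or data cut. Report therapy during and after elranatamab separately.
- For Objectives 6 and 3, label the present results as on-treatment. Add a supplementary analysis with a fixed tail after the last dose (30 or 90 days, for example), the same for inpatient and outpatient last doses and cut at death, last record or data end. Report it also with the tail cut at the start of the next MM treatment.
- Align the abstract, Table 2 and Tables 5, 6 and 8, check Figure 1, and add the truncation to Section 9.9.

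The cost is wording and some programming on data already held. Two downsides should be stated. Some tail events will reflect later therapy, which the second version of the tail addresses. And MDV follows patients only within one facility (Section 9.9), so transplant or CAR-T at another hospital stays unseen and the last hospital record may itself be an informative end point.

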9.3.1 Exposure Groups and Assessment Periods

[Table 1](#) outlines the variables to define exposure groups that will be used to identify patients and stratify analyses.

Table 1. Variables for Exposure

Variable	Role	Data Source	Operational Definition	
			Definition	Assessment Period(s)
Study population	Exposure	MDV	All patients with MM who have a hospital claim for elranatamab after March 26, 2024, and who meet the inclusion and exclusion criteria outlined in Sections 9.2.1 and 9.2.2.	Index date
SUD Exposure Group	Exposure	MDV	
Group A: Complete and timely SUD period
 
Patients in the study population with two 44mg/1.1mL vials (second 44mg/1.1mL vial is received 1 to 7 days after the first) and one subsequent 76mg/1.9mL vial between 1 to 7 days after second 44mg/1.1mL vial
 
Group B: Complete but not timely SUD period
 
Patients in the study population with two 44mg/1.1mL vials and one subsequent 76mg/1.9mL vial after the second 44mg/1.1mL vial, with one or both intervals between doses ranging from 8 to 14 days.
 
Group C: Alternative SUD period
 
 • Only one 44mg/1.1mL vial: patients in the study population with only one 44mg/1.1mL vial prior to receiving a 76mg/1.9mL vial • More than two 44mg/1.1mL vials: patients in the study population with more than 	SUD period

090177e1a4a71ff1\Approved\Approved On: 05-Nov-2025 14:15 (GMT)

Variable	Role	Data Source	Operational Definition	
			Definition	Assessment Period(s)
			
two 44mg/1.1mL vials prior to receiving a 76mg/1.9mL vial
 
 Extremely untimely: patients in the study population with more than 14 days between the first and second 44mg/1.1mL vial or between the second 44mg/1.1mL vial and the first 76mg/1.9mL vial 
Note that patients who received only 44mg/1.1mL vials or only 76mg/1.9mL vials are not classified under any SUD exposure group but will remain part of the study population.
	

Figure 2 illustrates possible elranatamab administration scenarios for each SUD group. These examples are not exhaustive and do not represent all potential administration schedules.

090177e1a4a71ff1\Approved\Approved On: 05-Nov-2025 14:15 (GMT)

Figure 2. SUD Periods Administration Schedule

[figure not shown]

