Table 2 summarizes the patient exposure groups and assessment periods during which endpoints for each study objective will be measured. Patients will be included in the follow-up sub-period analyses if they have at least one claim for elranatamab or if the end date of their follow-up period falls within the sub-period's time frame.

Table 2. Patient Exposure Groups Stratification and Assessment Period for Study Objectives

Study Objective	Assessment period	Patient Exposure Groups
Objective 1 – Patient Characteristics	Baseline period	Study population
	Index date	Group A, Group A+B, Group C
Objective 2 – Treatment administration, dosing and timing	SUD period 
 Overall (Between first 44mg/1.1mL vial – first 76mg/1.9mL vial) Between first 44mg/1.1mL vial – second 44mg/1.1mL vial Between second 44mg/1.1mL vial – first 76mg/1.9mL vial 	Group A, Group A+B, Group C
	Follow-up period 
 Index date 	Study population

090177e1a4a71ff1\Approved\Approved On: 05-Nov-2025 14:15 (GMT)

Study Objective	Assessment period	Patient Exposure Groups
	
 • Index date (day 1) to day 8 • Day 9 to day 168 • Day 169 to end of follow-up period • Overall (day 1 to end of follow-up period) 	
Objective 3 – HCRU and costs	HCRU baseline assessment period	Study population
	SUD period 
 • Overall (Between first 44mg/1.1mL vial – first 76mg/1.9mL vial) • Between first 44mg/1.1mL vial – second 44mg/1.1mL vial • Between second 44mg/1.1mL vial – first 76mg/1.9mL vial 	Group A, Group A+B, Group C
	Follow-up period 
 • Index date • Index date (day 1) to day 8 • Day 9 to day 168 • Day 169 to end of follow-up period • Overall (day 1 to end of follow-up period) 	Study population
Objective 4 – Other MM treatments including supportive therapy	Follow-up period 
 • Index date • Index date (day 1) to day 8 • Day 9 to day 168 • Day 169 to end of follow-up period • Overall (day 1 to end of follow-up period) 	Study population
Objective 5 – Known adverse events	CRS/ICANS follow-up assessment period (CRS/ICANS events)	Group A, Group A+B, Group C
	SUD period (Cytopenia events) 
 • Overall (Between first 44mg/1.1mL vial – first 76mg/1.9mL vial) 	Group A, Group A+B, Group C

090177e1a4a71ff1Approved\Approved On: 05-Nov-2025 14:15 (GMT)

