Acetaminophen	Outcome	MDV	Health claim code for acetaminophen (Yes/No)	SUD period
Tocilizumab	Outcome	MDV	Health claim code for tocilizumab (Yes/No)	SUD period

Variable	Role	Data Source	Operational Definition	
			Definition	Assessment Period(s)
IVIG	Outcome	MDV	Health claim code for IVIG (Yes/No)	IVIG follow-up assessment period

Abbreviations: IVIG: intravenous immunoglobulin; SUD: step-up dosing.

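### Objective 5 promises CRS and ICANS over the step-up period, but they are measured for 14 days from index, a window that covers different dose steps in the groups tabulated

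*Protocol*

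**What the plan says.** Objective 5 (protocol Section 8, repeated on the study information page and in the abstract) reads: "To describe incidence and prevalence of cytokine release syndrome (CRS), immune effector cell associated neurotoxicity syndrome (ICANS), and cytopenias during the SUD period". Section 9.2 defines the SUD period patient by patient, as the time between the "first 44mg/1.1mL vial of elranatamab and first 76mg/1.9mL vial of elranatamab, inclusive".

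Section 9.2 then gives CRS and ICANS a different window: "CRS/ICANS follow-up assessment period: defined as the 14-day window post index date", shortened if fewer days of data exist. Table 2 and Table 7 apply this window to every CRS and ICANS variable and keep the SUD period only for cytopenias.

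Table 2 reports these results for Group A, Group A+B and Group C. Table 1 and Table 12 (Annex 2) define the groups by the spacing and number of vials. Group A has both intervals at 1 to 7 days. Group B has two 44 mg vials and then a 76 mg vial, "with one or both intervals between doses ranging from 8 to 14 days". Group C collects patients with one 44 mg vial, with more than two, or with an interval beyond 14 days (the extremely untimely).

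**The concern.** There are two problems. First, the objective and the measurement name different periods. The amendment log shows that assessment periods for Objective 5 were added on purpose in version 2.0, but the current objective still names the SUD period for all three event types.

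Second, a window anchored at index interacts with strata defined by how long the steps took. In a timely schedule the 14 days take in the whole step-up and usually some days after the first 76 mg vial. In a delayed schedule they may stop before that vial is given. Events after the later steps can then be counted in one column of the table and not in another. Someone comparing columns could take a difference made by the window for a difference in safety. Nothing else planned would show this: Section 9.7.6 rules out sensitivity analyses, and the low-weight subgroup in Section 9.7.5 repeats Objective 5 and so inherits the window.

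**Working it through.** The protocol gives no figure on this point to reproduce, so the check enumerates the schedules that its definitions permit.

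**Inputs**
- d1 = whole days from first to second 44 mg vial; d2 = whole days from second 44 mg vial to first 76 mg vial. Index is the first 44 mg vial, so the first 76 mg vial falls at index + d1 + d2.
- Group A (Table 1): d1 and d2 both 1–7.
- Group B (Table 1): d1 and d2 both 1–14, at least one of them 8–14.
- Group C, extremely untimely: d1 or d2 above 14 (Table 1), or 14 and above (Table 12).
- Window end: Section 9.2 does not say whether index counts as a day of this window, so both index+14 and index+13 are tried.

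**Ranges, which need no weighting**
- Group A: 1+1 = 2 to 7+7 = 14 days.
- Group B: 8+1 = 9 to 14+14 = 28 days.
- Extremely untimely: at least 15+1 = 16 days, or 14+1 = 15 under Table 12. Both exceed 14, so the first 76 mg vial is always after the window. If d1 itself exceeds 14, so is the second 44 mg vial.
- Group C with one vial or more than two: no timing limit, so no range can be derived.

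**Counts, each permitted pair weighted equally (an assumption)**
- Pairs: A = 7×7 = 49; A+B = 14×14 = 196; B = 196−49 = 147.
- d1+d2 ≤ 14: 1+2+…+13 = 91 pairs, of which 49 are A and 42 are B.
- d1+d2 ≤ 13: 1+2+…+12 = 78 pairs, of which 48 are A and 30 are B.

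| First 76 mg vial after the window | Window to index+14 | Window to index+13 |
|---|---|---|
| Group A | 0/49 (0%) | 1/49 (2.0%) |
| Group B | 105/147 (71.4%) | 117/147 (79.6%) |
| Group A+B, as reported | 105/196 (53.6%) | 118/196 (60.2%) |
| Group C, extremely untimely | all | all |

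With the window ending at index+14, the mean number of window days left after the first 76 mg vial is 6.0 in Group A and 0.5 in Group B.

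**How far this depends on the weighting (window to index+14).** If only one interval is delayed and the on-time one is k days, then k of the 7 delayed values (8 to 14) put the first 76 mg vial outside. For k = 1 to 3 that is 1/7 to 3/7, fewer than half. Over all k and both orders it is 2×(1+2+…+7) = 56 of 98 (57.1%). If both intervals are delayed, the earliest is 8+8 = 16 days, so 49 of 49 fall outside; 56+49 = 105, as above.

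**Would the SUD period be better?** It ends on the day of the first 76 mg vial, so it leaves no day after that vial in any group. The gap it spans also runs from 2–14 days in Group A to 9–28 in Group B.

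**The case against.** The best defence is that a fixed window from initiation is a legitimate descriptive choice, made deliberately in an amendment after clinical input. With complete data every group is watched for the same 14 days, and Sections 9.1 and 9.7 exclude statistical comparisons between groups. On this view the only defect is an objective whose wording was not updated. The defence stands as far as it goes: the window need not be abandoned, and the stakes are lower in a secondary descriptive objective. But results laid out in columns by step-up timing invite comparison, and nothing in the tables would show how many patients had reached the first 76 mg vial.

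Four stronger readings are tempting, and the documents do not support them.

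- A reader might infer that the groups are followed for unequal time. They are not; what differs is the dose steps covered.
- A reader might take 71–80% as the share of delayed patients affected. The protocol gives no distribution of intervals, so it is a share of permitted schedules only. Group B is also never reported alone.
- A reader might conclude that delayed or alternative step-up is bound to look safer. Group C includes patients with a single 44 mg vial and no timing requirement, who may reach 76 mg early and have more observed time after it than Group A. The protocol also gives no event risk by dose step.
- A reader might add that tocilizumab and dexamethasone are counted over the SUD period, so that treatment and event windows clash. Table 7 already records medication given on the day of a CRS or ICANS event, within the event window. Table 9 serves a separate exploratory objective and may use its own period.

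**Conclusion.** The point holds and should be fixed. That the objective and the measurement name different periods is certain from the text. That the 14-day window covers different dose steps by group is also certain, because it follows from the definitions: the first 76 mg vial is at 2–14 days in Group A, at 9–28 days in Group B, and always beyond the window in extremely untimely Group C. The shares of 0–2% (A), 71–80% (B) and 54–60% (A+B) rest on equal weighting of whole-day schedules and on the two readings of the window's last day; they illustrate scale and do not estimate patients. A lower CRS or ICANS count in delayed schedules can therefore arise from the window alone. How many events would be missed, and in which direction pooled Group C would move, cannot be determined from the protocol.

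**What to change.** 1. Reword Objective 5 wherever it appears so that it names the 14-day window for CRS and ICANS and the SUD period for cytopenias. Say whether the window's last day is index+13 or index+14. Restoring the SUD period for CRS and ICANS would not solve the problem.
2. Keep the 14-day window, and report beside it, for each group, the number of patients whose first 76 mg vial falls inside it.
3. Add a display of CRS and ICANS by dose step (after the first 44 mg, second 44 mg and first 76 mg vial), with the same pre-specified post-dose length in all groups. Where the next vial comes before that length is over, show the days at risk in the step.

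The cost is small: a change of wording and one more derived window in claims already held. The main weakness is that assigning an event to a step depends on accurate claim dates, and Section 9.9 warns that timing errors matter most over short periods. The new display should carry that caveat.
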